## 1 STUDY SYNOPSIS

| Complete Protocol Title       | Allofit IT Ceramic Bearing System in Total Hip Arthroplasty
A multi-centre, prospective, non-controlled post market
surveillance study  |
|-------------------------------|---|
| Protocol Number               | CME2010-24H   |
| Short Protocol Title          | Allofit IT Ceramic Bearing System in THA  |
| Sponsor                       | Zimmer GmbH   |
| Manufacturer                  | Zimmer GmbH   |
| Study Device(s)               | 
 
Allofit IT Shell in combination with:
 
Ceramic-on-Ceramic Articulation: BIOLOX delta Taper Liner and BIOLOX delta Femoral Head
 
Femoral Component: Alloclassic® Zweymuller® Hip Stem, CLS® Spotorno® Stem or Fitmore® Stem
 
  |
| Study Objectives/Endpoints    | The objectives of this study are to obtain survival and outcome data on the Allofit IT Shell in combination with the BIOLOX® delta Taper Liner when used in primary total hip arthroplasty. This will be done by analysis of standard scoring systems, radiographs and adverse event records. Data will be used to monitor pain, mobility, and survivorship, and to confirm the safety and efficacy of the Allofit IT Ceramic Bearing System. Evaluation of squeaking and ceramic fracture rate will be an additional objective, the latter by evaluating by Adverse Events.  Safety will be evaluated by monitoring the frequency and incidence of adverse events.  Performance will be determined by evaluating survivorship, pain and functional performances, subject quality-of-life and radiographic parameters.  Survivorship will be based on removal or intended removal of the device Pain and functional performance will be measured using the Harris Hip Score, subject quality-of-life will be determined by evaluation of the EQ-5D and SF12, and radiographic parameters by analysis of x-rays. |
| Indications/Target Population | Patients, suffering from severe hip pain and disability requiring total hip arthroplasty, who meet the inclusion/exclusion criteria.  |
| Inclusion/Exclusion Criteria  | 
 
Inclusion Criteria
 
Patient is 18 to 75 years of age, inclusive.
 
Patient is skeletally mature.
 
Patient qualifies for primary unilateral or bilateral total hip arthroplasty (THA) based on physical exam and medical history including the following:
 
Avascular necrosis (AVN)
 
   |

- Osteoarthritis (OA)
- Inflammatory arthritis (i.e. Rheumatoid arthritis)
- Post-traumatic arthritis
   Patient has no history of previous prosthetic
   replacement device (any type, including surface replacement arthroplasty, endoprosthesis, etc.) of the affected hip joint(s).
- Patient has a Harris Hip Score <70 in the affected hip
- Patient is willing and able to provide written informed consent.
- Patient is willing and able to cooperate in the required post-operative therapy.
- Patient is willing and able to complete scheduled follow-up evaluations as described in the Informed Consent.
- Patient has participated in the Informed Consent process and has signed the Ethics Committee approved informed consent.

#### **Exclusion Criteria**

- The patient is:
  - A prisoner
  - Mentally incompetent or unable to understand what participation in the study entails
  - A known alcohol or drug abuser
  - Anticipated to be non-compliant.
- The patient has a neuromuscular disorder, vascular disorder or other conditions that could contribute to prosthesis instability, prosthesis fixation failure, or complications in postoperative care.
- The patient has a vascular (large and small vessel disease) insufficiency.
- The patient has a neurologic condition in the ipsilateral or contralateral limb which affects lower limb function.
- The patient has a diagnosed systemic disease that could affect his/her safety or the study outcome.
- The patient is known to be pregnant.
- The patient is unwilling or unable to give informed consent, or to comply with the follow-up program.
- The patient has received an investigational drug or device within the previous 6 months.
- The patient has an active or latent infection in or about the affected hip joint or an infection distant from the hip joint that may spread to the hip hematogenously.

|                                | 
 
The patient has insufficient bone stock to fix the component. Insufficient bone stock exists in the presence of metabolic bone disease (i.e. osteoporosis), cancer, and radiation. Note: Dual Energy X-ray Absorptiometry (DEXA) may be used to assess the presence of adequate bone stock.
 
The patient has osteoradionecrosis in the operative hip joint
 
The patient has a known sensitivity or allergic reaction to one or more of the implanted materials.
 
The patient has known local bone tumors in the operative hip.
 
The patient is Grade III obese with a Body Mass Index (BMI) > 40.
 
 |
|--------------------------------|--|
| Study Design                   | Multicentre, Prospective, Non-controlled   |
| Clinical Phase                 | Post-market  |
| Sample Size                    | A total of 200 patients were planned  185 patients were implanted with the study device and included in the study  |
| Length of Study                | 12 years (2 years of enrollment (all sites) and 10 years of follow-up)   |
| Materials and Methods          | Case report forms will be completed at Pre-op, Surgery, Discharge, and the 6 month, 1-year, 2-year, 3-year, 5-year, 7-year and 10-year intervals.  |
| Data Collection                | Paper/Electronic   |
| Statistical Reporting          | Data collected will be summarized and reported to each participating investigator. Statistical analysis will be conducted by Zimmer Biomet or its designee. Survivorship will be evaluated using Kaplan-Meier.   |
| Scores/Performance Assessments | Harris Hip Score (HHS); UCLA activity score; SF12; EQ-5D-3L, Noise questionnaire   |
| Standards                      | 
 
The PMCF is compliant with the below:
 
ISO 14155: 2020 - Clinical investigation of medical devices for human subjects - Good clinical practice. *
 
The Declaration of Helsinki (DoH) - Ethical principles for medical research involving human subjects.
 
(*) The study protocol was drafted according to another version of the ISO 14155. Adverse Event definitions and reporting are according to ISO 14155:2020.
 
   |
| Study Funding                  | Funding for this clinical study is made available by Zimmer Biomet to support clinical data collection, IRB/EC review fees and other expenses associated with the conduct and execution of this study protocol as outlined in the fully executed Clinical Trial Agreement.   |

Allofit IT Ceramic Bearing System in THA Protocol number: CME2010-24H

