#### 2 STATISTICAL ANALYSIS PLAN

## 2.1 Analysis Objectives

The assessment of efficacy for subjects receiving the total hip replacement system will be determined using the overall pain score and functional performance. Clinical success will be defined as a modified Harris Hip score of > 80 that included a rating of 'mild', or 'no pain'; a failure will be defined as a modified Harris Hip score < 80. Any study hip that required a subsequent surgical intervention where a stem head, cup, or liner was removed, or where a removal was planned, was considered a failure regardless of the Harris Hip score. Success rates will be expressed as percentages and primary summary results will be presented in tables which will contain the number and percentage of patients classified as a clinical success for the treatment group.

The assessment of safety will be evaluated by monitoring the frequency and incidence of adverse device effects in investigational subjects. As part of the safety profile, a survival analysis will be done.

The endpoints that contributed to the composite success will be summarized separately, that is, the Harris Hip Score. Additionally, there are measures of interest which will be used to assess the investigational device such as radiographic success, all components included in the assessment of radiologic success, the SF-12 patient satisfaction scores, patient activity scores, concomitant medication usage, and incidence of adverse events.

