### 2.2 Sample Size Justification

Sample size for the Allofit Ceramic PMCF Study was estimated using the McHugh and Le method [39] with an alpha (Type I) error level of 0.05, a non-inferiority margin of 5.2% ( $\delta$ ), and an assumed survival rate of 90% at 10 years from ODEP.

The confidence limit approach, as discussed by McHugh and Le [39], can be used to calculate this sample size estimate. Specifically, we infer that the non-inferiority margin provides the absolute precision (5%  $\delta$ ) for the difference between the fixed rate in the historical control group and the rate estimated for the experimental group over the course of the study. Sample size estimation utilizes the following formula:

$$\delta \sqrt{n} = Z_{1-\alpha} \sqrt{\frac{p_{\text{exp}} (1 - p_{\text{exp}})}{w_{\text{exp}}} + \frac{p_{HC} (1 - p_{HC})}{w_{HC}}}$$

where  $\delta$  represents the non-inferiority margin, n represents the group size,  $p_{exp}$  represents the rate in the experimental group,  $p_{HC}$  represents the rate in the historical control group,  $w_{exp}$ 

represents a weight (i.e., allocation weight) to accommodate unequal group size for the experimental group,  $w_{HC}$  represents the allocation weight to accommodate unequal group size for the historical control group, and  $Z_{1-\alpha}$  represents the value of a standard normally distributed random variable corresponding to a cumulative probability of one minus alpha (0.05).

When adjusting for a ceiling in the calculation, and added attrition rate of 20% there is a sample size requirement of 195 for the experimental group. A sample size of 200 is therefore planned for enrolment in this study.

Sample size was estimated using SAS v. 9.1.3 for Windows.

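### Does section 2.2 need a new precision figure because 185 patients were included, not the 195 required or the 200 planned?

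*Combined protocol and SAP*

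**What the plan says.** The Sample Size row of the synopsis (section 1) gives a plan of 200 patients and then the outcome of enrolment: "185 patients were implanted with the study device and included in the study".

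Section 2.2 describes the planning calculation. It works "with an alpha (Type I) error level of 0.05", a 90% survival rate at 10 years, and a margin given first as 5.2% and then as 5%. It reports that with an "added attrition rate of 20% there is a sample size requirement of 195 for the experimental group", and concludes: "A sample size of 200 is therefore planned for enrolment in this study". The figure 185 does not appear there. The prose refers to a "fixed rate in the historical control group", while the printed formula includes a variance term for that group, with allocation weights that are not stated.

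On analysis, the Statistical Reporting row of the synopsis says "Survivorship will be evaluated using Kaplan-Meier". Section 2.1 adds clinical success percentages and places a survival analysis within the safety profile. Neither place describes a comparison of the result with the margin in section 2.2.

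**The concern.** The synopsis was updated with the final enrolment, but the sample size section of the same document was not. The achieved cohort is 10 below the stated requirement and 15 below the target, and section 2.2 does not comment on this. It is the only place that ties the number of patients to a precision for 10-year survival. A reader could therefore set the final estimate against 5% or 5.2% and assume that the study was large enough to deliver it. If the shortfall decided whether that precision was attainable, the omission would matter.

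**Working it through.** **Inputs.** From section 2.2: one-sided level 0.05, so z = 1.645; margin 5.2% or 5%; survival 0.90; attrition 20%; 195 required; 200 planned. From the synopsis: 185 included. Assumptions, because the documents do not settle them: the experimental rate equals the historical rate (0.90), equal weights in the two-term formula, binomial variance, and one hip per patient.

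**The plan's own figure.** Solving the printed formula for n gives n = z² × k × 0.09 / δ², with k = 1 for a fixed historical rate and k = 2 for two terms with equal weights.

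| Reading | δ | n | n / 0.8 | n × 1.2 |
|---|---|---|---|---|
| Fixed | 5.2% | 90.05 → 91 | 114 | 110 |
| Fixed | 5% | 97.40 → 98 | 123 | 118 |
| Two terms | 5.2% | 180.10 → 181 | 227 | 218 |
| Two terms | 5% | 194.80 → 195 | 244 | 234 |

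With these inputs, 195 appears only for two terms at 5% with no attrition added. That is a separate matter. It counts here because 195 is not a firm benchmark for judging 185.

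**Half-width at each size.** Half-width = 1.645 × √(k × 0.09 / m), where m is the number remaining: 185, 195 or 200 without loss, and 148, 156 or 160 after 20% loss.

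| Reading | Loss | 185 | 195 | 200 | 185 vs 195 | 185 vs 200 |
|---|---|---|---|---|---|---|
| Fixed | 0 | 3.63 | 3.53 | 3.49 | 0.09 | 0.14 |
| Fixed | 20% | 4.06 | 3.95 | 3.90 | 0.11 | 0.16 |
| Two terms | 0 | 5.13 | 5.00 | 4.94 | 0.13 | 0.20 |
| Two terms | 20% | 5.74 | 5.59 | 5.52 | 0.15 | 0.22 |

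(All in percentage points; differences taken before rounding.)

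At equal loss the ratio does not depend on the reading: √(195/185) = 1.027, a widening of 2.7%. If 195 is taken at face value, 5.2 becomes 5.34 and 5.0 becomes 5.13.

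**Does the shortfall decide anything at the plan's 20% loss?** With a fixed rate, both 5% and 5.2% are met at all three sizes. With two terms, both are missed at all three. The answer depends on the reading of the formula, not on 185 against 195.

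**At other losses.**
- Fixed rate: 185 meets 5.2% up to a loss of 1 − 91/185 = 50.8%, and 5% up to 1 − 98/185 = 47.0%.
- Two terms, 5.2%: the limit is 1 − 181/185 = 2.2% for 185, 1 − 181/195 = 7.2% for 195 and 1 − 181/200 = 9.5% for 200.
- Two terms, 5%: 195 evaluable patients are needed. 185 cannot reach this, 195 reaches it only with no loss, and 200 up to 1 − 195/200 = 2.5%.

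The shortfall changes the answer only under the two-term reading, and only at losses below 10%, less than half of what the plan assumes.

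**Evaluable numbers.** If attrition was applied by dividing by 0.8, 195 stands for 156 evaluable patients, and 185 keeps that number up to a loss of 1 − 156/185 = 15.7%. If it was applied by multiplying by 1.2, 195 stands for about 163, and the limit is about 12%. Section 2.2 does not say which was used, so neither figure is a firm threshold.

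**The case for a change.** The best case for a change is that the synopsis gives the count but not its consequence, and that one added sentence would cost nothing in enrolment, visits or data. Under the two-term reading, 185 patients cannot reach 5% even with complete follow-up (5.13), whereas 195 just can (4.997). If 195 is taken at face value, 185 falls short of the stated precision by construction.

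The facts in this stand: 185 is below the stated requirement, and section 2.2 gives no precision for it. The case for acting on them is weak, for three reasons.

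- The two-term contrast holds only at losses well below the 20% that the plan allows over ten years. The face-value contrast is 0.13 to 0.14 points, measured from a figure that the stated inputs do not reproduce.
- The sentence could not be written without first choosing the margin, the fixed or two-term reading, and the weights. Those choices belong to the question of how 195 was obtained. Without them the addition would be mostly blanks.
- A revised planning half-width would not tell the reader the precision of the result. The standard error of the Kaplan-Meier estimate will come from the events and censoring observed in these 185 patients. The planning assumptions matter more than the shortfall: with 148 patients and a fixed rate, an illustrative 85% survival gives 1.645 × √(0.1275/148) = 4.8 points, against 4.06 at 90%. That difference is about 0.8 points, while the shortfall costs 0.11.

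**Conclusion.** No change to the plan is needed on this point. Section 2.2 records why 200 was chosen, such a justification is normally left as written once enrolment has closed, and the synopsis states openly that 185 were included. The shortfall against 195 costs about 0.1 to 0.15 points of half-width, and against 200 about 0.14 to 0.22. At the plan's 20% loss it does not alter whether 5% or 5.2% is met under either reading. The analysis text describes no test against the margin, and analysts will report the precision actually obtained from the Kaplan-Meier estimate.

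This rests on 90% survival, a one-sided 5% level, equal weights in the two-term reading and one hip per patient. Bilateral patients are eligible and the number of hips is not given, so correlation within patients is ignored. Treating 20% as lost outright is only a rough stand-in for censoring. It should not be called conservative without adding that survival is near 90%, loss is no more than 20%, censoring is non-informative and hips are independent. If section 2.2 is ever revised to show how 195 was obtained, a line for 185 could be added then, but nothing in the planned analysis depends on it.

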#### 2 STATISTICAL ANALYSIS PLAN

## 2.1 Analysis Objectives

The assessment of efficacy for subjects receiving the total hip replacement system will be determined using the overall pain score and functional performance. Clinical success will be defined as a modified Harris Hip score of > 80 that included a rating of 'mild', or 'no pain'; a failure will be defined as a modified Harris Hip score < 80. Any study hip that required a subsequent surgical intervention where a stem head, cup, or liner was removed, or where a removal was planned, was considered a failure regardless of the Harris Hip score. Success rates will be expressed as percentages and primary summary results will be presented in tables which will contain the number and percentage of patients classified as a clinical success for the treatment group.

The assessment of safety will be evaluated by monitoring the frequency and incidence of adverse device effects in investigational subjects. As part of the safety profile, a survival analysis will be done.

The endpoints that contributed to the composite success will be summarized separately, that is, the Harris Hip Score. Additionally, there are measures of interest which will be used to assess the investigational device such as radiographic success, all components included in the assessment of radiologic success, the SF-12 patient satisfaction scores, patient activity scores, concomitant medication usage, and incidence of adverse events.

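### Do the success and failure definitions leave some patients unclassified, and does the lack of a two-hip rule undermine the success rate?

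*Combined protocol and SAP*

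**What the plan says.** Section 2.1 (Analysis Objectives) gives three rules:

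- Success: "Clinical success will be defined as a modified Harris Hip score of > 80 that included a rating of 'mild', or 'no pain".
- Failure on score: "a failure will be defined as a modified Harris Hip score < 80". No pain condition is attached.
- Override: "Any study hip that required a subsequent surgical intervention where a stem head, cup, or liner was removed", or where removal was planned, "was considered a failure regardless of the Harris Hip score".

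The primary summary table reports the "number and percentage of patients classified as a clinical success for the treatment group". The override therefore works at the level of the hip and the table at the level of the patient. The inclusion criteria in the Study Synopsis admit patients who qualify for one or both hips, and they take the entry Harris score in the affected hip.

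The synopsis names the instrument without the word modified: "Pain and functional performance will be measured using the Harris Hip Score". Section 2.1 uses the name both with and without that word.

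**The concern.** A binary endpoint should assign every assessed case to exactly one class. Here success carries a pain condition and failure does not, and both score limits are written as strict inequalities, so the two classes do not cover all cases. Separately, if both hips of a bilateral patient are study hips and one succeeds while the other loses a component, the patient has one hip under each definition, and nothing in the supplied text says which result the patient receives. The denominator of the percentage is not written down either.

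This is the rule behind the table of primary summary results. If the gaps mattered, the same data could give different success rates, and a patient with a removed component could appear as a clinical success.

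**Working it through.** The plan states no success rate, expected or required, so there is no figure to reproduce. The check is to apply the rules literally and then bound the effect.

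**Step 1: classify one hip.** Three score classes, two pain classes and removal yes or no give 3 x 2 x 2 = 12 combinations.

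| Score | Pain | No removal | Removal done or planned |
|---|---|---|---|
| below 80 | none or mild | failure | failure |
| below 80 | worse | failure | failure |
| exactly 80 | none or mild | no label | failure |
| exactly 80 | worse | no label | failure |
| above 80 | none or mild | success | failure (override) |
| above 80 | worse | no label | failure |

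Three of the 12 combinations have no label, all without removal. The one combination that meets both definitions is settled as a failure by the override. If the success limit were in fact 80 or above, the two cells with worse pain and a score of 80 or more would still have no label.

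**Step 2: effect of the unlabelled cells on the table.** Let N be the patients assessed, s the successes and u the unlabelled patients. None of the u meets the success rule as printed: 80 is not above 80, and worse than mild pain is neither mild nor none. The numerator is therefore s however the u are labelled. Only the denominator can differ:

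- all assessed patients: s/N
- labelled patients only: s/(N - u)

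The difference is s*u / [N(N - u)]. Because s cannot exceed N - u, it is at most u/N, and it reaches that only if every labelled patient succeeds. With all assessed patients in the denominator it is zero.

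**Step 3: put numbers in.** The synopsis gives 185 implanted patients. Applying the 20% attrition from Section 2.2 to these gives 0.80 x 185 = 148. The range u = 1 to 5 is an assumption.

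| N | u = 1 | u = 5 |
|---|---|---|
| 185 | 1/185 = 0.54 points | 5/185 = 2.70 points |
| 148 | 1/148 = 0.68 points | 5/148 = 3.38 points |

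These are upper bounds.

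**Step 4: two hips, one patient.** A discordant bilateral patient can be counted either way, so each one moves the rate by 1/N, the same 0.54 or 0.68 points. For scale only, assume that 10% to 20% of patients have two study hips, that each hip succeeds with probability 0.90, and that the hips are independent. None of these assumptions is in the documents.

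- Both hips must succeed: 0.90 x 0.90 + 0.10 x 0.81 = 89.1%, and 0.80 x 0.90 + 0.20 x 0.81 = 88.2%.
- Either hip is enough: 0.90 x 0.90 + 0.10 x 0.99 = 90.9%, and 0.80 x 0.90 + 0.20 x 0.99 = 91.8%.

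The gap is 1.8 to 3.6 points. Independence makes it large; it falls to zero if a patient's two hips always agree.

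**The case for a change.** The strongest case for a change is that the pain gap and the hip-to-patient gap do not depend on how an inequality sign was printed, that they sit in the rule for the primary summary table, and that a few sentences would close them at almost no cost. For a discordant bilateral patient, two analysts could indeed reach different results from the text supplied.

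The literal reading stands: three cells have no label, and no two-hip rule appears in the synopsis or in Sections 2.1 and 2.2. Its consequences are much weaker.

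- The cell at exactly 80 exists only if both signs are truly strict. The text was extracted from PDF, and a lost bar under a sign cannot be excluded.
- The cell above 80 with worse than mild pain may be empty. The documents give no item weights, so it cannot be shown that anyone can fall there.
- The bilateral case requires both hips to be in the study, their results to disagree, and an analyst to credit the patient with success although one study hip failed. The documents show none of these. Nor would a removed component be hidden: the plan has a separate survival analysis, and the synopsis bases survivorship on removal, done or intended.
- The word modified is a matter of labelling. Section 2.1 uses both names for what reads as the same measure, and no classification is shown to change.
- Clustered standard errors would be relevant to estimates made per hip, and no such analysis is specified.

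**Conclusion.** The concern does not call for a change. The wording is incomplete, but no stated rule is shown to give a wrong result. For the score and pain cells the success count is fixed by the printed definition, and the percentage is fixed once all assessed patients form the denominator. Treating every other assessed case as a non-success is what an analyst would do. For bilateral patients a convention is missing, and the obvious cautious one, success only if every study hip succeeds, is within ordinary analyst judgement.

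The total effect cannot be determined from the documents, which give neither the number of scores at 80 nor the number of patients with two study hips. It is bounded by 0.54 points per affected patient at N = 185, or 0.68 at N = 148, and is probably small. The study is non-controlled, no test or threshold is attached to the success rate, and the sample size rests on 10-year survival, so no stated decision depends on a shift of this order. The conclusion rests on the signs as printed, on assessed patients being the denominator, and on the supplied sections being all that can be read; a longer document might already state the two-hip rule.

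### Does the clinical success percentage need a stated missing-data rule, visit and bilateral rule before it can be reported?

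*Combined protocol and SAP*

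**What the plan says.** Section 2.1 (Analysis Objectives) defines success as a modified Harris Hip score above 80 with mild or no pain, and states that "a failure will be defined as a modified Harris Hip score < 80". A separate rule covers surgery: "Any study hip that required a subsequent surgical intervention where a stem head, cup, or liner was removed", or for which removal was planned, is a failure whatever the score. The main tables then give "the number and percentage of patients classified as a clinical success for the treatment group".

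Three other places bear on how that percentage would be formed:

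- **Population and visits.** The Study Synopsis (Section 1) says in its Sample Size row that "185 patients were implanted with the study device and included in the study". Its Materials and Methods row lists follow-up at "the 6 month, 1-year, 2-year, 3-year, 5-year, 7-year and 10-year intervals".
- **Bilateral cases.** The inclusion criteria in the same section read: "Patient qualifies for primary unilateral or bilateral total hip arthroplasty (THA) based on physical exam".
- **Attrition and survival.** Section 2.2 (Sample Size Justification) gives "an assumed survival rate of 90% at 10 years from ODEP" and "added attrition rate of 20% there is a sample size requirement of 195 for the experimental group".

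The Statistical Reporting row of the synopsis names Kaplan-Meier for survivorship. Neither the synopsis nor the SAP attaches a target value, threshold or test to the clinical success rate.

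**The concern.** A percentage needs a denominator, and Section 2.1 leaves parts of it open. It does not say whether patients lost to follow-up stay in as failures or drop out. It does not say which of the seven post-discharge visits the rate belongs to. The removal rule classifies hips while the table counts patients, and nothing links the two when a patient has two study hips with different outcomes.

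The study has no control group, so the success rate is read on its own, and no second arm would share the same counting choice. With 20% attrition, a rate calculated on all 185 implanted patients cannot exceed 148/185 = 80.0%, so it would partly measure follow-up. A rate calculated only on hips that have a score would leave out removals, which the plan calls failures. If these choices were all open, someone who had seen the data could pick the most flattering figure.

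**Working it through.** The plan states no expected success percentage, so there is no figure of its own to reproduce. The check is how far the rate moves under each reading.

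**Inputs**

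- N = 185 patients implanted (Study Synopsis, Sample Size row).
- A = 0.20 attrition (Section 2.2).
- S = 0.90 device survival at 10 years (Section 2.2).
- h = share of unrevised, examined hips that meet the success definition. **This is an assumption**; the documents give no value. It is varied from 0.80 to 1.00.
- Also assumed: one hip per patient, and attrition independent of removal.

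**Formulas**

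- All implanted, missing counted as failure: S × h × (1 − A)
- All examined, removals counted as failures: S × h
- Unrevised, examined hips only: h

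**Example at h = 0.90.** Examined: 185 × 0.80 = 148. Unrevised and examined: 148 × 0.90 = 133.2. Successes: 133.2 × 0.90 = 119.9. The three rates are 119.9/185 = 64.8%, 119.9/148 = 81.0% and 119.9/133.2 = 90.0%.

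| h (assumed) | All implanted | All examined | Unrevised examined only |
|---|---|---|---|
| 0.80 | 57.6% | 72.0% | 80.0% |
| 0.85 | 61.2% | 76.5% | 85.0% |
| 0.90 | 64.8% | 81.0% | 90.0% |
| 0.95 | 68.4% | 85.5% | 95.0% |
| 1.00 | 72.0% | 90.0% | 100% |

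**Which readings the text allows.** The last column leaves out removed hips. Section 2.1 counts them as failures regardless of score, so that column contradicts the plan. Two readings remain, and they differ by S × h × A = 0.18h: 14.4 points at h = 0.80, 16.2 at 0.90 and 18.0 at 1.00.

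**Variant.** If removals are also known among the lost patients, there are 185 × 0.10 = 18.5 removals, and known status covers 18.5 + 133.2 = 151.7 patients. The rate at h = 0.90 is 119.9/151.7 = 79.0%, close to the 81.0% above.

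**Sampling error, for scale.** 1.96 × √(0.81 × 0.19/148) = 6.3 points. The gap between the two remaining readings is larger than this.

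**Unit.** The table's unit is stated: patients. The open question is the bilateral patient with one success and one failure. With bilateral share b and independent hips of success probability p, requiring both hips rather than either hip changes the rate by b × 2p(1 − p). With b = 0.05 and p = 0.90 that is 0.9 points; with b = 0.20 and p = 0.80 it is 6.4 points. Both b and p are assumed, since the documents give no bilateral count. Correlation between a patient's hips makes the difference smaller.

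**Score of exactly 80.** Success needs more than 80 and failure less than 80, so a score of 80 without removal has no label. The table reports successes, and a score of 80 is not one, so the count is unaffected.

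**Can the reader see the choice?** The tables give a number with each percentage. A count of 120 shown as 81.1% implies 120/0.811 = 148; the same count shown as 64.9% implies 120/0.649 = 185.

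**The case for a change.** The strongest case for changing the plan is that these tables carry the main efficacy result, that the two readings left open differ by 14 to 18 points, and that the gap exceeds the 6.3-point half-width. Survivorship has Kaplan-Meier to deal with incomplete follow-up, whereas the success rate has no matching rule. One paragraph in Section 2.1 would settle it without new data.

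Part of this stands. The text has no rule for lost patients, names no visit and does not link hips to patients, and the two denominators do give clearly different numbers. A report that gave the rate without its denominator would be hard to interpret.

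The rest is weaker. The 65% and 81% figures do not follow from the plan's 20% and 90% alone; they need an assumed score success rate. The two figures also answer different questions, so a gap wider than sampling error does not make either of them wrong. A removal is already a failure, so the reading that flatters the device most is closed. With repeated visits, a table by visit is the ordinary presentation, and a patient with a failed study hip would ordinarily not be counted as a success. A new paragraph would mostly write down that practice. Where it went further, for example by making the hip the main unit or 10 years the main visit, it would replace the plan's choices with a reviewer's preference.

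**Conclusion.** No change is called for. Section 2.1 is less complete than it could be, but none of its stated rules gives a wrong result. The success rate is a descriptive summary with no threshold or test, and the sample size does not depend on it. The ordinary way to fill the gap is to report by visit among patients with known status and keep removals as failures. That follows the rules already in the plan, and the printed counts make any other denominator visible.

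At the plan's 20% attrition and 90% survival, the choice of denominator is worth 14 to 18 points at ten years, about 65% against 81% when score success in unrevised, examined hips is taken as 90%. This rests on that assumed rate (80% to 100% for the range), on attrition independent of removal, and on one hip per patient. The bilateral question adds at most 6.4 points under assumed bilateral shares of 5% to 20% and hip success of 80% to 90%. The label for a score of exactly 80 is a clerical slip with no effect on the success count.
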